9.0 Study Population

1. Inclusion Criteria:
 1. Subject is able and willing to provide informed consent
 2. Subject is ≥ 20 and ≤ 85 years of age

PROTOCOL TITLE:

VERSION DATE:

3. Subject with diagnosis of Hypertension for a minimum of 1 year
4. Subject has been on the same class/classes of blood pressure medication for a minimum of 6 months. Note: A change in dosage, frequency, or specific medication is acceptable as long as there have been no changes to the class/classes of medications prescribed.
5. Subject with a Body Mass Index (BMI) ≥ 19 and ≤ 45
6. Subject is currently prescribed and taking one of the following classes of medications alone or in combination with each other.
 - o Diuretics (thiazide or thiazide-like)
 - o ACE Inhibitors
 - o Angiotensin Receptor Blocker (ARB)
 - o Beta-blockers
 - o Ca+ Channel Blockers

2. Exclusion Criteria:

1. Subject has a diagnosis of secondary hypertension or is experiencing a complication of pregnancy.
2. Subject is currently prescribed and taking any additional class of medication(s) for high blood pressure not included in the list above
3. Subject has Systolic BP > 190 or Diastolic BP > 120 documented within the six months prior to visit.
4. Any other reason that the subject is inappropriate for study enrollment in the opinion of the Investigator.

2. Screening:

Because this is a retrospective chart review study, subjects will be screened by a Fairview employee (or AHC personnel) for eligibility. Only subjects who have opted in (or who have not opted out) of research will be contacted.

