All patients with available data will be included in the analyses of the study objectives. No patients will be directly contacted to retrieve missing data, and no sensitivity analyses will be performed on missing data.

2. Power Analysis:

Power Calculation and Sample Size:

Given the unique study design and pilot/feasibility nature of this proposal, highly accurate preliminary data are not available to generate detailed power calculations on the impact of the Geneticure panel for hypertension therapy. This is due to the lack of studies that have been performed in a prospective manner on genetic guidance for hypertension. However, previous work from our group utilizing a relatively small sample size and chart review have yielded data on all

PROTOCOL TITLE:

VERSION DATE:

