17 genes that are contained within the Geneticure panel for hypertension treatment. Several of the genes with large effects can demonstrate statistical differences at relatively small sample sizes. For instance position 49 of the beta-1 adrenergic receptor demonstrates a functional genotype mean arterial blood pressure of 97mmHg (SD of 12.4mmHg) with beta-blocker therapy and the non-functional genotype demonstrates a mean arterial blood pressure of 102mmHg (SD of 11.5mmHg) with this same therapy. A power calculation based on this site of the beta-1 adrenergic receptor would yield a sample size per group needed of 109 for an alpha level of 0.05 and a power of 0.80 (not correcting for multiple comparisons) (table 1). Based on these results we can determine that the gene with the smallest effect from this previous smaller study (specifically that encoding WNK-1, rs2107614) will determine the approximate sample size needed to observe an effect, if an effect exists, for the panel as a whole in this prospective trial. Data from our phase-I trial demonstrates a mean arterial blood pressure of 97.6mmHg with diuretic therapy in the functional genotype group of WNK-1 and a mean arterial blood pressure of 100.8mmHg (Pooled SD = 12) with diuretic therapy in the non-functional genotype group for this site of WNK-1. Without correcting for multiple comparisons, one can determine that a per-group sample size of 162 individuals would be needed for 80% power with an alpha of 0.01. Using an alpha of 0.05 and a power of 0.80 we have estimated that we will need 300 subjects per group to observe a significant difference, where one exists. Based on possible retention of 70% of subjects who initially enroll, we will seek to recruit up to 2000 subjects for the study.

Concomitant Medications/Treatment/Procedures

This study protocol does not require change to any existing treatments or those prescribed during the course of the study by the Investigator or any other provider whom the subject sees for any medical reason. Outside of eligibility screening, there are no clinical evaluations planned as part of this study.

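### The per-group sample sizes do not follow from their printed inputs, and the 300 per group appears to be a contrast among diuretic users although the 600 analysed may take any of five drug classes

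*Combined protocol and SAP*

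**What the plan says.** Section 16.0, Power Analysis, gives three per-group sizes, each at 80% power.

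- **ADRB1, position 49, on beta-blocker.** Means 97 and 102 mmHg, SDs 12.4 and 11.5. This "would yield a sample size per group needed of 109 for an alpha level of 0.05 and a power of 0.80", with a note that multiple comparisons are not corrected for and a reference to a table 1 that is not in the available text.
- **WNK-1, rs2107614, on diuretic.** A "mean arterial blood pressure of 97.6mmHg with diuretic therapy in the functional genotype group of WNK-1", against 100.8 mmHg in the non-functional group, pooled SD 12. Without correction, "a per-group sample size of 162 individuals would be needed for 80% power with an alpha of 0.01".
- **Final figure.** "Using an alpha of 0.05 and a power of 0.80 we have estimated that we will need 300 subjects per group". This sentence names no gene, drug or effect.

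WNK-1 is described as the smallest effect, and the section says that it "will determine the approximate sample size needed to observe an effect, if an effect exists, for the panel as a whole".

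Section 11.0 calls 600 subjects ideal, and the Data Analysis Plan in section 16.0 sets an initial analysis at up to 600, with tests corrected for the number run. Section 9.0 admits users of five classes: "Subject is currently prescribed and taking one of the following classes of medications alone or in combination with each other". On recruitment, section 16.0 says "Based on possible retention of 70% of subjects who initially enroll, we will seek to recruit up to 2000 subjects"; section 11.0 adds co-morbidities as a reason, without a rate.

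**The concern.** At equal power and for one effect, a smaller alpha always needs more subjects. The plan prints 162 at 0.01 and 300 at 0.05, so a reader cannot tell what the smallest-effect gene requires.

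The larger issue is who is being counted. The inputs that set the size are genotype groups among diuretic users, and 2 × 300 = 600 matches the number to be analysed. Nothing in the plan reserves those 600 for diuretic users or sets a number per class or per genotype. If only part of the 600 take a diuretic, the WNK-1 contrast has fewer subjects than the calculation assumes, and a null result at 600 could be read as evidence against an effect that the analysis had little chance of detecting.

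**Working it through.** **Inputs.** All means, SDs, alphas and powers are those printed in section 16.0. Sidedness and allocation are not stated; I take two-sided tests and equal groups unless noted. This is the two-group comparison of mean arterial pressure (MAP) on which the plan bases its own sizing, not the regression in the Data Analysis Plan.

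**Formula.** n per group = 2(z₁₋α/₂ + z₀.₈₀)² / d², then refined with the exact two-sample t solution.

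**WNK-1.** d = 3.2/12 = 0.267, d² = 0.0711.
- Alpha 0.05: 2 × (1.960 + 0.842)² / 0.0711 = 220.7; exact t 221.7.
- Alpha 0.01: 2 × (2.576 + 0.842)² / 0.0711 = 328.5; exact t 330.1.

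**ADRB1.** Pooled SD = √[(12.4² + 11.5²)/2] = 11.96; d = 5/11.96 = 0.418. Alpha 0.05: 89.8; exact t 90.8.

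| Contrast | Alpha | Plan | From inputs | Power at the plan's n |
|---|---|---|---|---|
| ADRB1 | 0.05 | 109 | 91 | 87% |
| WNK-1 | 0.01 | 162 | about 330 | 43% |
| WNK-1 (inferred) | 0.05 | 300 | 222 | 90% |

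**Attempts to reproduce the plan's figures.** None of the three follows from its printed inputs.
- One-sided testing at 0.01 still needs 284, not 162.
- Swapping the two alphas gives 222 against 162 and 330 against 300.
- 162 is about half of 330. Even at alpha 0.05 it gives only 67% power.
- 300 is close to what 90% power at 0.05 needs (296.5), or 80% power at 0.05/3 (295.9). Neither is stated.
- One common margin does not explain both conservative figures: 300/222 = 1.35, 109/91 = 1.20.

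**Denominator.** With a fraction p of diuretic users in one genotype group, the total needed is (z₁₋α/₂ + z₀.₈₀)² / [d² p(1 − p)]. At alpha 0.05 the exact t totals are 443.4 (50/50) and 527.5 (30/70). Dividing by the number analysed gives the diuretic share needed for 80% power: for example 443.4/600 = 74% and 527.5/600 = 88%. The other cells follow in the same way, with 1400 = 0.70 × 2000. Splits, test counts and Bonferroni are my assumptions.

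| Alpha | 600, 50/50 | 600, 30/70 | 1400, 50/50 | 1400, 30/70 |
|---|---|---|---|---|
| 0.05 | 74% | 88% | 32% | 38% |
| 0.05/3 | 99% | not reachable | 42% | 50% |
| 0.05/18 | not reachable | not reachable | 59% | 71% |

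If 60% of the 600 take a diuretic (assumed) with equal genotype groups, power is 71% at 0.05, 55% at 0.05/3 and 32% at 0.05/18. With all 600 on a diuretic and equal groups it is 90%, 81% and 60%.

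**Recruitment.** 600/0.70 = 857.1, so 858. Retention of 70% does not lead to 2000.

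**The case against.** The strongest reply is that the one clear error has no effect on size. The 162 is not used, and 300 exceeds what its apparent inputs need. That stands: the arithmetic defect misleads the reader but does not shrink the study.

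The 300 sentence also drops the no-correction wording that precedes 162, so it may include an unstated margin or correction. That is possible, and it is why the plan should state its basis. It does not rescue 162, which directly follows the WNK-1 means and SD and comes with its own alpha, power and lack of correction. The 109 is an illustration that errs on the safe side and may be explained by the missing table.

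The link from 300 to diuretic users is inferred from sentence order and from the statement that WNK-1 sets the size. That too is fair; if another contrast was meant, the plan needs to name it. The background describes diuretics as the usual first drug, and combinations are allowed, so the diuretic share could be high, but no percentage is given.

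The 600 is an initial analysis, 2000 is a ceiling, and section 16.0 concedes that "highly accurate preliminary data are not available to generate detailed power calculations". All true. A pilot may rest on rough assumptions, but this one still uses these figures to set its size. Whether the earlier means and SDs apply to patients with controlled pressure was not examined here; the check takes them as printed.

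**Conclusion.** The concern holds. The 162 per group is wrong as written: its inputs need about 330 (284 one-sided), and it has 43% power. The 300 and 109 do not follow from the inputs shown (222 and 91) but err on the safe side.

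The conditional claim about the denominator also holds. If, as it appears, the 300 are diuretic users, 80% power for WNK-1 at 600 requires roughly three-quarters or more of the subjects to take a diuretic, before any correction for multiple tests. The planned correction lowers power further, by an amount that depends on a test count the plan does not give. The full cohort of up to 1400 retained may be adequate; the analysis at 600 is the exposed one.

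The arithmetic on 162 is certain. The size of the shortfall rests on the assumed class shares, genotype splits, test counts and Bonferroni correction. This should be fixed, but it is not a reason to change enrolment.

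**What to change.** Keep the enrolment number and revise the power analysis in section 16.0.

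1. Replace the figures with about 222 (alpha 0.05) and about 330 (alpha 0.01) per group for WNK-1 and about 91 for ADRB1, or state the added assumptions that give 300 and 109. State sidedness.
2. Add a small table of power, or detectable MAP difference, at 600 and at 1400 retained, for a stated range of diuretic share and genotype split, uncorrected and at the corrected alpha for a stated number of tests. For scale, at 60% on a diuretic (assumed) with equal groups, the detectable differences at 0.05, 0.05/3 and 0.05/18 are 3.55, 4.11 and 4.88 mmHg at 600, and 2.32, 2.68 and 3.18 mmHg at 1400.

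Two clarifications would help but matter less: say that the per-group numbers refer to users of the relevant class, alone or in combination, and say what enrolment beyond about 858 is for.

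The cost is text edits and one table, with no extra patients or procedures. The stated power for the analysis at 600 will look less favourable.

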16.0 Data Management

1. Data Analysis Plan:

The Investigator is responsible to ensure the accuracy, completeness, and timeliness of reported data.

PROTOCOL TITLE:

VERSION DATE:

All data will be compiled within the Fairview system on secure servers. De-identified final data may be sent to Geneticure using a secure, password-protected Excel spreadsheet on a server that is only accessible to IRB-approved personnel and is fully auditable. The database will be validated prior to use in the study. All required data will be recorded on CRFs or paper facsimiles. Data collected within the CRFs will be supported by source documents as appropriate and may be updated to reflect the latest observations on the subjects participating in the study. Corrections to the source documentation will be made in a manner that does not obscure the original entry and will be dated and initialed by the Investigator or assigned designee. It is important for data entry to occur in a timely manner, therefore, data collected on source documents should be transferred into CRFs as soon as possible following study visits.

All data will be coded for statistical analysis (i.e. drug classes will be coded numerically and genotypes will be coded numerically). Subject's raw genetic data will be entered into the Geneticure for Hypertension algorithm. All data will be analyzed with SPSS v.20. Normality of the data will be assessed using Levene's test prior to statistical analysis and any correction for non-normal data distribution will be used. Descriptive statistics will be computed (average time for blood pressure control, average number of visits to the clinician for blood pressure control, age, height, weight, BMI, etc.).

Data will be initially analysed following the collection of samples/data from up to 600 subjects. Statistical tests will be corrected for the number of tests run (preservation of alpha). Ordinary least squares regression via univariate modelling will be used to estimate the magnitude of linearity between drug class that yielded the best blood pressure control and genetic profile of the subject. Multiple regression analysis will be performed to determine the impact of confounding variables (height, weight, age, race) on blood pressure control. For all statistical analyses an alpha level of 0.05 will be used to determine statistical significance.

Missing Data

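### The 300 per group is sized at alpha 0.05 with no multiplicity adjustment mentioned, while the analysis plan promises one; the stated 80% power is lost once more than three tests are corrected for

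*Combined protocol and SAP*

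**What the plan says.** **Sizing (Section 16.0, Power Analysis).** The variant with the smallest effect in the group's previous study, WNK-1 rs2107614, "will determine the approximate sample size needed to observe an effect, if an effect exists, for the panel as a whole". The first input is a "mean arterial blood pressure of 97.6mmHg with diuretic therapy in the functional genotype group of WNK-1". The comparison is with non-functional carriers on the same drug class, whose mean is given as 100.8 mmHg; the pooled SD is 12. Two sample sizes follow. The first is at alpha 0.01: "Without correcting for multiple comparisons, one can determine that a per-group sample size of 162 individuals would be needed". The second is the operative one: "Using an alpha of 0.05 and a power of 0.80 we have estimated that we will need 300 subjects per group". The no-correction wording goes with the 162, and with the 109 given for the beta-1 receptor. The sentence with the 300 does not say whether its alpha is corrected.

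**Analysis (Section 16.0, Data Analysis Plan).** The multiplicity rule reads "Statistical tests will be corrected for the number of tests run (preservation of alpha", and the paragraph ends "For all statistical analyses an alpha level of 0.05 will be used to determine statistical significance". The plan does not name a family of tests, a number of tests or a correction method.

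**How many tests there might be.** The panel has seventeen variants in Section 2.0, 18 SNPs in Section 4.0 and 19 in Section 5.0. Section 3.0 lists two primary measures.

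**Which total counts.** Section 11.0 treats 600 subjects as the ideal number for analysis, and the Data Analysis Plan sets the initial analysis at up to 600. That matches 2 × 300. The 2000 is a recruitment ceiling.

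**The concern.** The power statement and the analysis plan appear to use different significance thresholds. Sizing on the weakest single SNP so that the panel as a whole is covered makes most sense if the variants are tested one by one. If each of those tests is then corrected for the number run, its threshold is well below 0.05 and its power is below what 300 per group gives at 0.05.

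A non-significant result for a variant would then be read as if it came from a test with 80% power, when the power could be nearer 60%. Because the family and method are not fixed in advance, the effective threshold could also be settled after the results are known.

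**Working it through.** **Inputs.** From Section 16.0, Power Analysis: means 97.6 and 100.8 mmHg, so Δ = 3.2; pooled SD σ = 12; n = 300 per group; alpha 0.05; power 0.80. Assumed because not stated: two-sided testing, equal groups, and Bonferroni (α = 0.05/m for m tests).

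**Step 1: the plan's own figure.**

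n per group = 2σ²(z₁₋α/₂ + z₀.₈₀)²/Δ² = 2 × 144 × (1.960 + 0.842)²/10.24 ≈ 221 (222 by t-test).

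So 300 does not reproduce at two-sided 0.05 and 80% power. It is close to the 296 needed for 90% power at 0.05, and to the 295 needed for 80% power at 0.05/3. The 162 does not reproduce either: alpha 0.01 and 80% power need 329 two-sided or 283 one-sided. The two figures also run the wrong way, since a stricter alpha cannot need fewer subjects.

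**Step 2: power of 300 per group at a corrected alpha.**

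Δ/(σ√(2/n)) = 3.2/(12 × √(2/300)) = 3.266, and power ≈ Φ(3.266 − z₁₋α/₂).

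| Tests m | α = 0.05/m | z | 3.266 − z | Power, normal | Power, t-test |
|---|---|---|---|---|---|
| 1 | 0.05 | 1.960 | 1.306 | 90.4% | 90.3% |
| 2 | 0.025 | 2.241 | 1.025 | 84.7% | 84.6% |
| 3 | 0.01667 | 2.394 | 0.872 | 80.8% | 80.6% |
| 4 | 0.0125 | 2.498 | 0.768 | 77.9% | 77.6% |
| 17 | 0.00294 | 2.974 | 0.292 | 61.5% | 61.0% |
| 18 | 0.00278 | 2.991 | 0.275 | 60.8% | 60.4% |
| 19 | 0.00263 | 3.008 | 0.258 | 60.2% | 59.7% |

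The crossing point is between three and four tests. Whether the panel has 17, 18 or 19 variants hardly matters. Sidak in place of Bonferroni gives 60% to 62% for 17 to 19 tests.

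**Step 3: per-group size for 80% power at the corrected alpha.** About 314 for four tests and 410 to 417 for 17 to 19 (normal approximation).

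**Step 4: does 600 overall mean 300 per group?** The WNK-1 difference is among patients on a diuretic, and Section 9.0 admits five drug classes. The documents give neither the share on a diuretic nor the genotype split. Two illustrations, each resting on an assumption:

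- Half of 600 on a diuretic, equal genotype groups (150 each): power about 63% at 0.05 and 24% at 0.05/18.
- All 600 on a diuretic, genotypes split 1:3 (150 and 450): about 81% at 0.05 and 43% at 0.05/18.

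**The case against.** **The 300 may already allow for some correction.** The document never calls it uncorrected; that would be an inference. Since only 221 are needed at plain 0.05, 300 has slack that absorbs a Bonferroni correction for up to three tests. This stands, and it is why the point is conditional on the number of tests. It does not rescue a per-variant correction, where power is about 60% on either reading of the 300.

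**The number of tests is not in the plan.** The Data Analysis Plan feeds the genotypes into an algorithm and regresses on the genetic profile; it does not specify 18 separate SNP tests. If the primary analysis were one algorithm-level test for each of two endpoints, the WNK-1 inputs would give about 85% at 300 per group. That is fair, but the plan does not say so, and the sizing argument is built on a single SNP.

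**Stronger readings that a reader might infer, and that the documents do not support:**

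- *That the two alpha sentences contradict each other.* They are compatible if 0.05 is the family-wise level or the threshold for adjusted p-values. The wording is incomplete.
- *That a false positive somewhere in the panel is more likely than not.* The figure 1 − 0.95¹⁸ = 60% requires ignoring the explicit correction sentence and treating the SNPs as independent. The 18 SNPs lie in 11 genes; if each gene acted as one test, 1 − 0.95¹¹ = 43%.
- *That about 830 subjects in total (2 × 415) would restore 80% at 0.05/18, comfortably under the ceiling of 2000.* That needs every subject to be on a diuretic and genotypes to split evenly. If half were on a diuretic, 830 subjects would give about 39%.

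**The stakes are limited.** The plan describes itself as pilot or feasibility work, results will not influence prescribing, and WNK-1 is the panel's smallest effect; for the beta-1 effect, power at 0.05/18 with 300 per group is about 98%. This lowers the urgency but does not make the stated power right.

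**Conclusion.** The concern holds in a conditional form. The sizing statement uses 0.05 with no adjustment mentioned, and the analysis plan promises an adjustment that it does not define. On the protocol's inputs, 300 per group keeps at least 80% power for up to three tests and loses it from the fourth. With one test per variant, power for the sizing SNP is about 60%.

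This rests on the protocol's 3.2 mmHg and SD of 12, two-sided testing, Bonferroni, and 300 diuretic users in each genotype group. If the groups are smaller or unequal, power is lower. The calculation compares two means, as the protocol's own sizing does, whereas the planned analysis is a regression. These figures are therefore not the power of the planned analysis itself.

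The failure of 300 and 162 to follow from their inputs is a separate fault. Correcting it would not settle the multiplicity question.

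**What to change.** **Section 16.0, Data Analysis Plan.** State that 0.05 is the two-sided family-wise level. Define the primary family as one algorithm-level test for each of the two primary endpoints, adjusted by Holm. Make SNP-level tests secondary, under Holm or a permutation maximum; the latter allows for correlation between SNPs in the same gene. Settle whether the panel has 17, 18 or 19 variants, so that the size of the secondary family is fixed.

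**Section 16.0, Power Analysis.** Restate the power of 300 per group at the corrected alpha: about 60% for an 18-SNP family on the WNK-1 inputs. Say that this assumes 300 diuretic users in each genotype group, which 600 subjects overall need not provide. Reconcile the 300 and the 162 with their stated inputs in the same edit. Do not replace them with a new total unless the diuretic share and genotype split behind it are stated.

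**Cost.** Wording only, and a less favourable stated power for single-SNP tests. The documents give no effect size for the algorithm-level test, so its power has to be based on a stated assumption or left open.

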11.0 Local Number of Participants

1. Local Number of Participants to be Consented: Up to 2000 subjects may participate in the study. 600 subjects are ideal for statistical analysis but given possible co-morbidities, we aim to consent up to 2000 individuals.

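### The sample size rests on a contrast within diuretic users, but the 600-subject target counts users of any of five drug classes, so the stated 80% power is not assured at the first analysis

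*Combined protocol and SAP*

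**What the plan says.** Section 16.0, Power Analysis, lets the marker with the smallest earlier effect (WNK-1, rs2107614) fix the size for the whole panel. The two means are "a mean arterial blood pressure of 97.6mmHg with diuretic therapy in the functional genotype group of WNK-1" and "100.8mmHg (Pooled SD = 12) with diuretic therapy in the non-functional genotype group". The requirement follows, at alpha 0.05 and power 0.80: "we have estimated that we will need 300 subjects per group to observe a significant difference, where one exists". The other worked example, the beta-1 receptor, is likewise confined to beta-blocker users.

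Section 11.0 says that "600 subjects are ideal for statistical analysis", with up to 2000 to be consented because of possible co-morbidities. The Data Analysis Plan in section 16.0 sets the initial analysis at up to 600 subjects. The Power Analysis justifies the 2000 by 70% retention.

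Eligibility (section 9.0, inclusion criterion 6) reads: "Subject is currently prescribed and taking one of the following classes of medications alone or in combination with each other". The list is thiazide-type diuretics, ACE inhibitors, ARBs, beta-blockers and calcium channel blockers. No section gives an expected share, minimum or target for any class, or for any class by genotype.

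**The concern.** In the power calculation a group is a set of diuretic users with a given WNK-1 genotype. In the recruitment target a subject is anyone on an eligible class. Moving from 300 per group to 600 in total treats the two as the same. That is true only if every patient takes a diuretic and the two genotype groups are equal in size. The eligibility rule does not ensure the first, and the second is set by genotype frequencies that the plan does not state.

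A patient on an ARB alone contributes nothing to the WNK-1 contrast under diuretic therapy. If many such patients are enrolled, a null WNK-1 result at the first analysis could mean no effect or simply too few diuretic users. A reader relying on the stated 80% power could not tell which.

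**Working it through.** **Inputs.** From section 16.0: difference 100.8 - 97.6 = 3.2 mmHg; pooled SD 12; alpha 0.05; power 0.80; retention 70% of 2000 = 1400. From sections 11.0 and 16.0: 600 subjects. Sidedness is not stated; two-sided is assumed. The diuretic share *s* and the genotype split are not in the documents, so a range is assumed.

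**1. The plan's own figure.** Standardised difference d = 3.2/12 = 0.267. Normal approximation, equal groups:

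n per group = 2 x (1.960 + 0.842)² x 12² / 3.2² = 221.

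The t-test version gives 222, or 444 in total. The stated 300 is not reproduced. With 300 per group, power is 90%; the t-test requirement for 90% power is 297. The stated inputs therefore set a requirement of 222 diuretic users per group, before the multiplicity correction that section 16.0 also calls for.

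**2. Diuretic share needed for 80% power.** With equal genotype groups:

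- at 600: 444/600 = 74%
- at 1400: 444/1400 = 32%

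With a 20:80 genotype split the total needed rises to about 692 diuretic users. That exceeds 600, so 80% cannot be reached at 600 even if everyone takes a diuretic (120 v 480 gives 74%). At 1400 it needs 692/1400 = 49%.

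**3. Power over assumed shares.** For a subject total N and smaller-genotype fraction g: n1 = N x s x g and n2 = N x s x (1 - g). Power comes from the two-sample t-test with noncentrality d x √(n1 x n2/(n1 + n2)). Example: N = 600, s = 40%, g = 0.5 gives 120 v 120 and noncentrality 0.267 x √60 = 2.07, hence power 54%.

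| Diuretic share (assumed) | 600, 50:50 | 600, 20:80 | 1400, 50:50 | 1400, 20:80 |
|---|---|---|---|---|
| 30% | 90 v 90: 43% | 36 v 144: 30% | 210 v 210: 78% | 84 v 336: 59% |
| 40% | 120 v 120: 54% | 48 v 192: 38% | 280 v 280: 88% | 112 v 448: 71% |
| 60% | 180 v 180: 71% | 72 v 288: 52% | 420 v 420: 97% | 168 v 672: 87% |
| 100% | 300 v 300: 90% | 120 v 480: 74% | 700 v 700: >99% | 280 v 1120: 98% |

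**4. Does the 2000 ceiling already allow for drug mix?** Retention alone would require 600/0.70 = 858 enrolled. The ceiling is well above that, but the reasons given are co-morbidities and retention, not drug exposure.

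**The case against.** The strongest reply is that the plan is not limited to 600. It may recruit up to 2000, and the 600-subject analysis is only the initial one. At 1400 retained, equal genotype groups reach 80% power with a diuretic share of only 32%. The share may also be high: section 2.0 describes diuretics as the usual first-line class, kept when others are added, and combinations are eligible. At 600 with an even split, a 75% share gives 81%. Section 16.0 also calls the work pilot/feasibility in nature and concedes that precise preliminary data are lacking.

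Most of this stands, and it limits the point. A reader might infer that only 600 patients will be recruited, that the informative groups will be far smaller than stated, or that the 80% power is simply false. The documents support none of these. The ceiling is 2000, and the size of any shortfall depends on a share and a split that they do not give. Nor is exposure unrecorded: medication history is abstracted and class and genotype are coded, so counts can be made. What is missing is a planned number.

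Nor are patients on other classes useless to the study. The main regression in section 16.0 relates the best-performing drug class to genetic profile, and they inform that. They add nothing only to the contrast on which the sample size rests.

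The reply does not rescue the 600 figure. It is offered as the right number for analysis, and it equals 2 x 300 only if nobody is outside the diuretic group.

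**Conclusion.** The point holds in a limited form. Total sample size is not linked to the number of diuretic users in each WNK-1 genotype group, so power for the contrast that justifies it is unknown. At the 600-subject analysis it is below 80% unless about 74% or more take a diuretic with an even genotype split; a less even split raises that threshold. Full recruitment may be enough, depending on the same two quantities.

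The structural mismatch is certain from the text. The power values rest on the plan's 3.2 mmHg and SD 12, two-sided 0.05, no multiplicity correction, and assumed shares and splits. Correcting for multiple tests would lower every value. This should be corrected before the first analysis, since a sample-size statement that the study relies on does not describe the sample it will have.

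**What to change.** - **Section 16.0, Power Analysis:** define a group as diuretic users within each WNK-1 genotype group. Correct the per-group requirement to match the stated inputs (222 at two-sided 0.05 and 80% power, 444 in total at 1:1), or state the inputs that give 300. Give the assumed diuretic share and genotype split with their source, and derive the total from them.
- **Section 11.0 and the first-analysis rule in section 16.0:** either make the trigger a count of diuretic users by genotype, within the existing ceiling of 2000, or keep 600 and state the power for the diuretic-exposed subset at that size.

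Do not add mailing targeted by drug class. The planned regression relates drug class to genetic profile, so recruiting by class would select on a variable under study. Restricting every marker to one paired class is not supported either, because the power section pairs only two markers with a class.

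The cost is protocol wording and a tally from data already being abstracted, with no increase over 2000. The downside is a less favourable stated power at 600, or a later first analysis.
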